### **3.3 Secondary Study Endpoints**

- **Assess the safety and tolerability of Avelumab + HFRT in adults with *IDH* mutant gliomas that have transformed to GBM after temozolomide or PCV chemotherapy.**

An important secondary objective of this study is to characterize the safety, toxicities and tolerability of Avelumab when administered with HFRT among subjects with transformed *IDH* mutant GBM beyond the Safety Lead-In. A safety analysis of the phase II portion of the trial will include all subjects who experience toxicities as defined by CTCAE 4.03 criteria. Safety will be assessed by quantifying the toxicities and grades experienced by subjects who have received Avelumab with HFRT, including serious adverse events (SAEs), immune-related adverse events (irAEs) and AESIs.

Safety will be assessed by reported adverse experiences using CTCAE, Version 4.03. The attribution to drug, time-of-onset, duration of the event, its resolution, and any concomitant medications administered will be recorded. AEs will be analyzed including but not limited to all AEs, SAEs, and fatal AEs. Furthermore, irAEs and AESIs will be collected and designated as adverse events as described in **Section 3.4** and **Section 5.2.3.3**. For statistical details of the **Primary Safety Endpoint** for the phase II trial, see **Section 3.4**.

- **Estimate the 12-month OS, median PFS, Response Rate, and median duration of response.**

To further define efficacy of Avelumab + HFRT in this study population, secondary measures of efficacy will be assessed, including 12-month overall survival (OS), median progression-free survival (PFS), the radiographic response rate and median duration of response. The subjects treated at the RP2D in the Safety Lead-In will be included as a separate cohort for the evaluation of outcomes in the phase II study. See **Statistical Methods, Section 7.2**, for details of these secondary study endpoints.

CONFIDENTIAL

- **Association of PFS6 with: hypermutation phenotype; proportion of predicted mutation-associated neoantigens among all somatic mutations; tumor PD-L1 expression; baseline and change in regulatory T cell (Treg) and myeloid-derived suppressor cell (MDSC) levels.**

For complete details of laboratory correlative secondary endpoints, including background and rationale, handling/shipping of research specimens and description of the methods, see **Attachment 7** and the **Lab Manual**.

### 3.4 Primary Safety Endpoints

For the overall endpoints of the Safety Lead-In portion of the study, see **Section 3.2.1**. Safety summaries will be reported for both the Safety Lead-in and the phase II trial. All subjects who received at least one dose of Avelumab and/or radiation will be used for the analysis of safety data in this study. Safety and tolerability will be assessed by clinical review of all relevant parameters including adverse experiences (AEs), laboratory tests, and vital signs.

For the phase II portion of the study, we consider a rate of toxicity of 40% or greater (defined as CTCAE grade 3, grade 4, or intolerable grade 2 toxicity that is possibly, probably, or definitely related to study therapy) to be unacceptable. We will conduct an interim assessment for safety after 10 patients are treated for at least 2 cycles (56 days) and again after 18 patients are treated for at least 2 cycles (56 days). If there are 7 or fewer unacceptable toxicities among the first 10 patients, the trial will continue and not be stopped for safety. After safety analysis of 18 patients, the trial will continue if there are 11 or fewer patients with an unacceptable toxicity. These analyses are not adjusted for multiple assessments and at each analysis, there is a 5% alpha level and 80% power. At the conclusion of the trial, with 43 patients, the trial would be considered to have an unacceptably high toxicity rate if 24 or more patients experienced the specified toxicities.

Due to a possible increased incidence of CNS toxicity from delayed radiation necrosis or radiation injury occurring during the first 6 months post RT, a special interim analysis will be performed. After the first 20 subjects treated at the RP2D, including subjects in the Safety Lead-In portion of the trial, have a minimum 24 week overall survival follow-up time from the end of RT, an interim safety analysis for delayed treatment-induced neurotoxicity will be performed. If the incidence of CTCAE grade  $\geq 3$  CNS (neurologic) toxicity deemed possibly, probably, or definitely related to treatment is 30% or higher in this group, the trial will be halted due to lack of safety.

Additionally, for safety summary purposes, specific **immune related adverse experiences (irAEs)**, as defined **Section 5.2.3.3**) and **adverse events of special interest (AESI)**, as defined below) will be collected and summarized in separate tables from other AEs by toxicity grade and will include the counts, percentage, and 95% CI. Any AE of unknown etiology associated with Avelumab exposure will be evaluated to determine if it is of a potentially immunologic etiology.

**Adverse events of special interest (AESI)** in this study will be defined as:

- Any AE that meets Dose-Limiting Toxicity (DLT) criteria (see **Section 5.2.1.2**)
- Grade 2 or greater infusion-related reactions (See **Section 5.2.3.5**)
- Grade 2 or greater allergic/hypersensitivity reactions (see **Section 5.2.3.5**)
- Grade 3 or greater symptoms suspected to be attributable to brain edema (see **Section 5.2.1.2** for **Rules for Brain Edema**).
- Grade 3 or greater immune-related toxicities (irAEs) (see **Section 5.2.3.3**)

All AESIs must be reported to the study **sponsor** within 24 hours of awareness of the event per **Section 8.3.1**. AESIs should be reported to the local institution's DSMC and IRB per local institution guidelines. If the AESI is **not** a DLT or SAE, there is no need to report to the DSMC or IRB within 24 hours unless specified by the local institution's DSMC or IRB.

CONFIDENTIAL

This material is the property of the NYU School of Medicine and Langone Medical Center. Do not disclose or use except as authorized in writing by the study sponsor

Adverse events (specific terms as well as system organ class terms) and predefined limits of change in laboratory, and vital sign parameters will be summarized with descriptive statistics (counts, percentage, mean, standard deviation, etc.). Continuous measures such as changes from baseline in laboratory, and vital signs parameters will be summarized using descriptive statistics (mean, standard deviation, etc.) for baseline, on-treatment, and change from baseline values.

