### Timeline of Selected Important Events

### 3.1.2 General Study Design

This is a multicenter, single arm, open label, phase II trial of Avelumab and radiation in adult patients with transformed *IDH* mutant GBM with the primary objective of estimating PFS6.

The study will start with a **Safety Lead-In (Section 5.2.1)**, which will be conducted to further define the safety and determine the recommended phase II dose (RP2D) of Avelumab in a subsequent expansion cohort when combined with HFRT. The Safety Lead-In also incorporates a de-escalation of Avelumab dosing if unexpected dose-limiting toxicity is observed in the first 6 subjects and follows a 3+3 phase I design. The first 6 subjects will be considered as a Safety Lead-In and will be observed for dose-limiting toxicities (DLTs) for an evaluation period of 28

CONFIDENTIAL

This material is the property of the NYU School of Medicine and Langone Medical Center. Do not disclose or use except as authorized in writing by the study sponsor

days. The dose of Avelumab administered during the Safety Lead-In will not exceed the established RP2D of Avelumab when administered as monotherapy.

The **Phase II trial (Section 5.2.2)** is a two-stage design study at the Avelumab dose determined to be safe in combination with HFRT (RP2D) in the Safety Lead-in. The phase II trial will enroll a total of 18 subjects in stage 1. In interim evaluation for efficacy will be conducted at the end of stage 1. If the efficacy measures are met, 25 additional subjects will be enrolled in stage 2 for a total planned enrollment in the phase II trial of 43 patients. Monitoring of toxicity will be carefully assessed during the phase II trial (see Primary Safety Endpoints, **Section 3.4**). For study purposes, the occurrence of toxicity attributable to Avelumab that requires discontinuation of Avelumab therapy as defined in **Section 5.2.3.2** is defined as unacceptable. Dose limiting toxicity rates of 40% or less are considered acceptable. Interim analyses of safety will be conducted at 10 patients and again at 18 patients as described in the Primary Safety Endpoints (**Section 3.4**).

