### 8.5 Stopping Rules

For the **Safety Lead-In**, see **Section 5.2.1, Safety Lead-In Treatment Regimen**, for detailed rules for continuing enrollment, dose decisions, and study discontinuation. In summary, once each cohort has filled enrollment, enrollment will stop and subjects will be observed for 28 days for dose-limiting toxicities (DLTs). At the end of each DLT period, the Safety Monitoring Team will review the safety data at a Safety Lead-In Dose Review meeting that will include at least a representative from each site; sub-investigators may be included. Continuation of enrollment will occur once all of the subjects have completed the Day 28 safety assessments of that particular cohort and the final dosing decisions, including whether the study should be discontinued or proceed to phase II, will be made by the Safety Monitoring Team.

For the Phase II trial, stopping rules for unexpected toxicity are outlined in see **Section 3.4, Primary Safety Endpoints**, and stopping rules for futility at the end of stage 1 of the phase II trial are outlined in **Section 7.2.2, Statistical Methods**.

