#### 8.6.1 Data and Safety Monitoring Committee

CONFIDENTIAL

This material is the property of the NYU School of Medicine and Langone Medical Center. Do not disclose or use except as authorized in writing by the study sponsor

This investigator-initiated study will be monitored by the Data Safety Monitoring Committee (DSMC) of the New York University (NYU) Perlmutter Cancer Center (PCC). The DSMC operates based on the 2011 National Cancer Institute approved Charter. It is an existing and multidisciplinary committee (consisting of clinical investigators/oncologists, biostatisticians, nurses, and research administration staff knowledgeable of research methodology and design and in proper conduct of clinical trials) that is responsible for monitoring safety, conduct and compliance in accordance with protocol data monitoring plans for clinical trials conducted in the NYULMC Perlmutter Cancer Center that are not monitored by another institution or agency. The DSMC reports to the Director of the NYULMC PCC. Per the NYU PCC Institutional Data Safety and Monitoring Plan, this phase 2 trial will be monitored by DSMC twice annually (from the date the first patient is enrolled), at dose escalation point and subsequent cohort activation, and at the completion of the study prior to study closure. This review includes accrual data, subject demographics and adverse events. Accrual to the next dose within a cohort will be held until real-time review of the toxicity from the prior cohort has occurred to assure no defined DLTs have occurred prior to proceeding to the next level or expanding the current cohort. Principal Investigators are required to attend the review of their studies. Additional reviews can be scheduled based on SAE reports, investigator identified issues, external information, etc. The DSMC will review safety data every 6-8 weeks.

Other external sites will be monitored and informed of other adverse events by the medical monitor within 7 days of toxicities and within 3 business days of SAE. Scheduled conference calls will be conducted after 3 patients are enrolled and at each dose escalation point. Additional conference calls will be scheduled as indicated based on the recommendations from the medical monitor, the Overall PI of this study.

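### After the 18-patient look, the general-toxicity limit is not read again until the conclusion of the trial at 43 patients, although the limit of 24 can be reached part-way through stage 2

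*Combined protocol and SAP*

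**What the plan says.** Section 3.1.2 splits phase II into 18 patients in stage 1, after which "25 additional subjects will be enrolled in stage 2 for a total planned enrollment in the phase II trial of 43 patients". It places the safety looks in stage 1: "Interim analyses of safety will be conducted at 10 patients and again at 18 patients".

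Section 3.4 gives the rules. It sets the threshold with the words "we consider a rate of toxicity of 40% or greater". The first look reads: "If there are 7 or fewer unacceptable toxicities among the first 10 patients, the trial will continue and not be stopped for safety". At 18 patients the trial continues with 11 or fewer patients affected. The final reading is "At the conclusion of the trial, with 43 patients, the trial would be considered to have an unacceptably high toxicity rate if 24 or more" of them have the specified toxicities.

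The same section adds a CNS rule. It is applied once the first 20 subjects treated at the RP2D, lead-in included, have 24 weeks of follow-up from the end of radiotherapy. The trial is halted if related grade 3 or higher neurologic toxicity is 30% or more.

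Section 8.5 adds no number of its own for phase II. It says that "stopping rules for unexpected toxicity are outlined in see" Section 3.4.

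On committee review, Section 8.6.1 says "this phase 2 trial will be monitored by DSMC twice annually (from the date the first patient is enrolled" and, later in the same paragraph, "The DSMC will review safety data every 6-8 weeks". Sections 8.6 and 10.1 say twice a year. Sections 9.4 and 10.1 give 6-8 weeks as the interval for quality-assurance monitoring.

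**The concern.** More than half of phase II exposure (25/43 = 58%) comes after the last interim look at general toxicity. No stage 2 patient's data enter any numerical interim rule. The plan's own count of 24 can be reached well before patient 43, so its verdict of excess toxicity can be settled while patients are still being enrolled, and nothing in Section 3.4 says to act on it then. What is at stake is the number of patients treated after the plan's own criterion has been met.

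**Working it through.** **Inputs.** All are from Section 3.4 unless stated:
- Boundary toxicity rate 0.40.
- Stop at 8 or more of 10, and at 12 or more of 18.
- Declare excess toxicity at 24 or more of 43.
- Stage sizes 18 and 25 (3.1.2).
- Stage 2 opens with 8 or more PFS6 successes in 18 (7.1.3).
- Radiotherapy on Days 8-12 (5.2.2).
- Six months = 168 days (7.2.2).

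Toxicities are treated as independent between patients, with a constant rate p.

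**Reproducing the plan's limits.** With X ~ Bin(n, 0.40):
- P(X ≥ 8 | n = 10) = 0.0123
- P(X ≥ 12 | n = 18) = 0.0203
- P(X ≥ 24 | n = 43) = 0.0260

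A limit one lower gives 0.0548, 0.0576 and 0.0507. Each limit is therefore the smallest that keeps the one-sided size at or below 5%. The plan also states 80% power at each analysis but names no alternative rate. That power needs true rates of about 0.843, 0.727 and 0.609, so no single alternative fits all three.

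**Passing both looks.** Exact recursion: P(pass) = P(X₁₀ ≤ 7 and X₁₈ ≤ 11). Final flag: P(pass and X₄₃ ≥ 24).

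| True rate | Stop at 10 | Stop at 18 | Pass both | Pass and 24+ of 43 | Share of passers declared too toxic |
|---|---|---|---|---|---|
| 40% | 0.0123 | 0.0148 | 0.973 | 0.0188 | 0.0188/0.973 = 2% |
| 50% | 0.0547 | 0.0817 | 0.864 | 0.1777 | 0.1777/0.864 = 21% |
| 60% | 0.1673 | 0.2300 | 0.603 | 0.3892 | 0.3892/0.603 = 65% |
| 70% | 0.3828 | 0.3539 | 0.263 | 0.2489 | 0.2489/0.263 = 95% |

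**When the verdict can be fixed.** A trial that passes has at most 11 events at patient 18. The 24th event then needs at least 13 more, so it comes at patient 18 + 13 = 31 at the earliest, with up to 12 patients still to enrol.

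**Reading the limit of 24 as events accrue.** Mean stage 2 exposure among trials that pass both looks is the sum over j = 0 to 24 of P(fewer than 24 events after 18 + j patients | passed). It is 22.7 at a 60% rate and 19.7 at 70%, against 25 under the plan. The savings are 25 − 22.7 = 2.3 and 25 − 19.7 = 5.3 patients. They assume each toxicity is known at once.

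**False positives at 40%.** 0.0123 + 0.0148 + 0.0188 = 0.0459. This does not change, because a trial reaches its 24th event by patient 43 exactly when it ends with 24 or more.

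**CNS look.** An RP2D rests on 6 lead-in subjects, so the 20 are those 6 plus phase II patients 1-14. The look falls at about Day 12 + 168 = Day 180 of patient 14. The 18-patient look falls at Day 57 of patient 18. The CNS look therefore comes later unless patient 14 started more than 180 − 57 = 123 days before patient 18.

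**The case against.** A reader might infer that stage 2 has no toxicity trigger at all, that the next rule after 18 patients is the final one, and that a too-toxic regimen is bound to reach everyone. The documents do not support this. The CNS rule is a written halting rule and will usually be read after the 18-patient look. The documents do not say that accrual pauses between stages, so it could be read while stage 2 patients are on treatment. It also targets the overlapping risk named in Section 1.5.3. The DSMC evaluates all SAEs (8.4) and may hold extra reviews (8.6.1), and adverse events are reviewed monthly (8.6). What remains is that none of this puts a number on general toxicity in stage 2.

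The pass probabilities must also not be read as the chance of reaching stage 2. The PFS6 gate stops 56% of trials at a true PFS6 of 40%. Section 7.1.3 counts patients who leave treatment before six cycles as failures, so toxicity feeds that gate. Assume 60% toxicity and a PFS6 of 60% apart from toxicity. The chance of clearing both safety looks and the gate is then 0.57 if no toxic patient leaves early, 0.35 if half do, and about 0.05 if all do. The shares leaving early are assumptions. This objection stands, and 0.60 is an upper bound.

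Finally, the saving is small and shrinks further if toxicity is ascertained late. The two interim looks wait 56 days per patient; if accrual continued over a similar wait, fewer patients would be spared.

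**Conclusion.** The point holds in a limited form. Between patients 18 and 43 there is no general-toxicity limit, and the one later halting rule is neurologic only and contains no stage 2 patient. At a 60% toxicity rate a trial passes both looks with probability at most 0.60, before the PFS6 gate. About 65% of those that pass, if they run to 43, would be declared too toxic only after everyone is treated, unless the DSMC steps in on judgement alone.

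The figures rest on independent events, the toxicity definition in Section 3.4, and immediate ascertainment. Section 3.1.2 defines unacceptable toxicity differently (events requiring discontinuation of avelumab) and calls a rate of 40% or less acceptable, where Section 3.4 calls 40% or more unacceptable. The two need reconciling so that the event being counted is clear.

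This is a cheap improvement, not a flaw that undermines the design.

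**What to change.** In Section 3.4, apply the existing limit of 24 as events accrue and not only at the conclusion. When the 24th phase II patient has a qualifying toxicity, hold accrual and refer to the existing DSMC, because the plan's own verdict is then fixed. Repeat the cross-reference in Section 8.5.

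In Sections 8.6, 8.6.1 and 10.1, state one DSMC review frequency and separate it from the 6-8 week quality-assurance interval.

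The cost is protocol wording and a running tally for an existing committee. The chance of stopping or declaring excess toxicity at a 40% rate stays at 4.6%. The downside is that efficacy data from the remaining patients may be lost if accrual does not resume. Whether to add a further stage 2 look, and at what limit, is for the sponsor and the DSMC; no new limit is proposed here.

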## 5.2.2 Phase II Trial

Following determination of the RP2D for Avelumab when combined with HFRT in the Safety Lead-In, subjects meeting eligibility criteria will receive Avelumab administered intravenously at the RP2D. A total of 43 patients are anticipated to be treated in the Phase II trial. The Phase II trial is a two stage design phase II trial with a planned interim analysis for futility and planned interim analyses for safety (see **Section 7.2.2** for **Statistical Methods**).

CONFIDENTIAL

The first dose of study agent (Avelumab) will be administered after all procedures / assessments have been completed as detailed on the Schedule of Events (**Attachment 1**). Avelumab will be administered IV at the RP2D established for administration with HFRT in the Safety Lead-In.

Beginning 7 days after the first dose of Avelumab (i.e. Day 8), all subjects will be administered HFRT to a total of 25 Gy, given in 5 fractions of 5 Gy on consecutive days (i.e., Day 8 to Day 12).

After the first dose, Avelumab administration will continue every 2 weeks. Avelumab administration will continue for up to 2 years or until the subject discontinues study therapy as per **Subject Withdrawal** guidelines (**Section 4.5**). Subjects who are discontinued from study therapy will enter the post-study follow-up phase of the study as per **Section 4.5.2**.

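### The delayed CNS-toxicity halt is judged once, at 24 weeks after radiotherapy for 20 subjects, with no trigger at the sixth confirmed event that already determines the result

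*Combined protocol and SAP*

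**What the plan says.** Section 3.4 sets a separate safety analysis for delayed neurotoxicity.

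- **Group:** "After the first 20 subjects treated at the RP2D, including subjects in the Safety Lead-In portion of the trial".
- **Timing:** once these subjects "have a minimum 24 week overall survival follow-up time from the end of RT, an interim safety analysis" is performed; only one is planned.
- **Boundary:** if the incidence of grade 3 or higher CNS toxicity judged at least possibly related to treatment "is 30% or higher in this group, the trial will be halted due to lack of safety".

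No alpha or power is given for this rule. The sentence "These analyses are not adjusted for multiple assessments and at each analysis, there is a 5% alpha level and 80% power" follows the general toxicity looks at 10 and 18 patients and describes those. Section 3.4 gives no earlier CNS look, no event count that triggers action, and no pause in enrolment while the 24 weeks accrue.

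On enrolment, Section 3.1.2 says "The phase II trial will enroll a total of 18 subjects in stage 1" and then "If the efficacy measures are met, 25 additional subjects will be enrolled in stage 2". This makes stage 2 conditional on the stage 1 result, but no accrual hold is written.

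**The concern.** The rule exists because CNS injury after re-irradiation may appear late, and Section 3.4 refers to the first six months after RT. With the group fixed at 20, the incidence cannot fall below 30% once six of them have a confirmed qualifying event, whatever happens to the other 14. The plan still waits until the last of the 20 has been followed for 24 weeks.

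No other numerical rule fills the gap. The DLT window is 28 days (Section 5.2.1.2). The general toxicity looks come after 56 days of treatment and stop only at 8 of 10 or 12 of 18, so six CNS events alone would trip neither. Section 8.5 refers back to Section 3.4 for phase II toxicity stopping. At stake is whether further subjects begin a regimen that has already met the plan's own criterion for lack of safety.

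**Working it through.** **1. The plan's boundary.** 5/20 = 25% and 6/20 = 30%. Six is the smallest count that meets the 30% criterion.

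**2. Probability of halting.** For true rate p, P(X ≥ 6) = 1 − Σ(k=0..5) C(20,k) pᵏ(1−p)²⁰⁻ᵏ:

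| True rate | 10% | 20% | 30% | 40% | 50% |
|---|---|---|---|---|---|
| P(6 or more of 20) | 0.011 | 0.196 | 0.58 | 0.87 | 0.98 |

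Acting at the sixth confirmed event gives the same probabilities, because it identifies the same set of trials. Only the timing differs.

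**3. Date of the planned look.** Section 5.2.2 gives HFRT "on consecutive days (i.e., Day 8 to Day 12"). RT therefore ends 11 days after the first dose, and 24 weeks is 168 days. The look falls 11 + 168 = 179 days after subject 20 starts.

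**4. Subjects who can still start.** Six lead-in subjects at the RP2D plus 18 in stage 1 make 24. If stage 2 waits for the stage 1 result, at most four start after subject 20. This holds provided subject 24 starts at least 11 days after subject 20, since the stage 1 endpoint is 168 days (six 28-day cycles, Section 7.2.2).

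**5. Accrual (assumption).** The documents give no rate. The Study Summary gives a study duration of about 24 months. Spreading 6 + 43 = 49 subjects over 24 or 18 months gives 2.0 or 2.7 per month. The range used is 2 to 4.

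**6. Time from sixth event to look.** This was simulated with random starts at the stated rate, a 28-day pause after the sixth lead-in subject, a 40% true rate, and starts capped at 24. Two event-timing assumptions were used, each uniform. The later one reflects Section 1.5.2, which places radiation necrosis at 3 months or more after RT. Results are means over trials with at least six events:

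| Starts per month | Events 0.5–5.5 months after RT: wait; further starts; trials with none | Events 3–5.5 months after RT: wait; further starts; trials with none |
|---|---|---|
| 2 | 5.6 months; 4.1; 25% | 4.4 months; 2.4; 45% |
| 2.7 | 4.8 months; 2.6; 44% | 3.6 months; 1.1; 70% |
| 4 | 4.0 months; 1.0; 72% | 2.8 months; 0.2; 94% |

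At a 30% true rate with the wider timing, further starts are 2.8 and 0.5 at 2 and 4 per month. If accrual runs straight into stage 2 (40% rate, events uniform over the 24 weeks), mean further starts are 11.7 and 16.2.

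**7. Early deaths.** Sections 1.1.1 and 7.1.1 give a median OS of 7–9 months. With exponential survival, the fraction alive 24 weeks (5.52 months) after RT, counting from the end of RT, is 0.5^(5.52/7) = 0.58 to 0.5^(5.52/9) = 0.65. If only 24-week survivors counted, about 20/0.65 = 31 to 20/0.58 = 35 treated subjects would be needed, and the sixth event would no longer settle the result. Section 3.4 does not say how such deaths are handled.

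**The case against.** **Existing oversight may act first.** Grade 3 or higher symptoms suspected to come from brain edema are AESIs that reach the sponsor within 24 hours (Sections 3.4 and 8.4.1). The DSMC evaluates all SAEs (Section 8.4). It reviews safety every 6–8 weeks (Section 8.6.1 also says twice annually) and can hold additional reviews. This stands: nothing prevents earlier action. But that action is discretionary, and none of these reviews carries a CNS boundary.

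**A reader might infer that patients will keep starting treatment for months after the boundary is crossed.** The documents do not support that as a certainty. The months in the table are the wait for the look, not a period of continued enrolment. Further starts depend on an unstated accrual rate and on event timing. If stage 2 waits, at 4 per month most halting trials have none.

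**A reader might infer that an automatic halt at the sixth reported event changes nothing but the date.** That does not follow. The Rules for Brain Edema in Section 5.2.1.2 allow an event first suspected to be pseudoprogression or CNS necrosis to be re-attributed to progression after further imaging, biopsy and consultation. A provisional six can become five, so a permanent halt on reported events could raise the probability of halting. The equality in step 2 holds for confirmed events only.

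**A reader might infer that the look may never take place, because subjects who die early never reach 24 weeks.** Survival follow-up runs until death (Sections 3.1.2 and 6.8), and Section 3.4 keeps every treated subject in the safety analysis. The natural reading is that a death completes follow-up. What remains is an ambiguity that one clause resolves.

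**Conclusion.** The point holds in a limited form. The delayed CNS rule has one formal judgement, no count trigger and no accrual hold, although a sixth confirmed event among a fixed 20 determines the result. At an assumed 40% true rate and 2 to 4 starts per month, the formal decision comes a mean of about 2.8 to 5.6 months after the boundary is met. Meanwhile a mean of about 0.2 to 4 further subjects start if stage 2 waits for the stage 1 result, and more if it does not. These sizes rest on assumed accrual, event timing and true rate, none of which the documents give. The 6-of-20 arithmetic and the halt probabilities rest only on the fixed denominator and confirmed attribution. This is a patient-safety improvement worth making. It does not affect the efficacy test.

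**What to change.** Amend Section 3.4, leaving the 30% threshold and the first 20 RP2D subjects unchanged:

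1. State the boundary as 6 or more of the first 20 RP2D subjects.
2. When a sixth qualifying event among them is reported, suspend enrolment for prompt DSMC review and attribution. Apply the existing halt once six events are confirmed under the existing relatedness definition.
3. Otherwise, do the planned analysis when each of the 20 has 24 weeks from the end of RT or has died, with early deaths kept in the denominator.

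The cost is a short amendment, a running count by the study statistician, and possibly a short enrolment pause that proves unnecessary if an event is later re-attributed to progression. The 24-hour AESI and SAE reporting already in place can feed the count. With confirmed events the halt probability stays at 0.58, 0.87 and 0.98 for true rates of 30%, 40% and 50%.
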